4.11.4 Vital Signs, Physical Findings and Other Observations Related to Safety

Vitals signs, ECG recording will be summarized for all visits scheduled in treatment and follow up periods. Unscheduled visits will be listed only, unless they contribute to baseline measurement.

Baseline is defined as the last evaluable measurement before first dose, including any unscheduled assessment.

Vital Signs

Following vital signs will be measured:

- Systolic blood pressure [mmHg]
- Diastolic blood pressure [mmHg]
- Pulse rate [beats/min]
- Body temperature (oral, tympanic or rectal) [°C or °F]
- Oxygen Saturation [%]

Investigators will assess each vital sign value and categorize either as clinically significant (CS) or not clinically significant (NCS).

Temperature values recorded as °F will be summarized as °C using the function below:

$$^{\circ}\text{C} = (^{\circ}\text{F} - 32) \times \frac{5}{9}$$

For body temperature measurements in degrees of Fahrenheit, both $^{\circ}\text{F}$ and $^{\circ}\text{C}$ values and units will be reported in line listings. Body temperature values obtained from different body parts will be summarized separately by measurement location in the order of oral, tympanic and rectal.

The following summaries for vital signs will be provided:

- A summary of each vital sign along with number and percentage of patient with CS vital sign by treatment group and visit.
- A summary of the change from baseline in each vital sign parameter by treatment group and visit.
- A summary of the number and percentage of patients with any CS vital sign value in each vital sign parameter by treatment group.

By-patient listing will be provided for all patient enrolled by visit, including changes from baseline and investigator's interpretations. A separate listing of potentially clinical important vital signs will be provided for assessments with any CS vital sign observation.

ECG

For each time point, an overall interpretation will be recorded by the Investigator as normal, abnormal not clinically significant, or abnormal clinically significant.

A summary of the number and percentage of patients in each category (normal, abnormal NCS and abnormal CS) will be provided by treatment group and visit.

By-patient listing will be provided for all patients enrolled. A separate listing of potentially clinical important ECG readings will be provided for ECG recordings assessed as CS.

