4.2. Eligibility Criteria

4.2.1. Inclusion Criteria

A patient will be eligible to participate in this study if ALL the following criteria are met:

1. Adult (≥ 18 years old) men or women, hospitalized or not hospitalized, diagnosed for SARS-CoV-2 infection by PCR or Rapid Antigen tests (approximately 48 hours prior to randomization), with at least one associated risk factor. Considered risk factors are:
 - Age ≥ 65 years
 - Obesity defined as BMI ≥ 30
 - Recent history of uncontrolled High Blood Pressure
 - Treated diabetes (type I or II)
 - History of ischemic cardiovascular disease
2. Symptomatic patients must present at least 1 of the following symptoms at enrollment: fever or perceived fever for more than 24 hours, headache, sore throat, dry cough, fatigue, chest pain or choking sensation (with no associated respiratory distress), myalgia, anosmia, ageusia, or gastro-intestinal symptoms.
3. Patients with pulse oximetry arterial saturation (SpO₂) $\geq 92\%$ on room air at enrolment.
4. Patients with the following hematological and biochemical laboratory parameters obtained within 7 days prior to D0:
 - Hemoglobin > 9.0 g dL⁻¹
 - Absolute Neutrophil Count ≥ 1000 mm⁻³;
 - Platelets $\geq 100,000$ mm⁻³;
 - Creatinine clearance ≥ 50 mL min⁻¹ by the Cockcroft-Gault formula
 - Total serum bilirubin $< 2 \times$ ULN
 - Alkaline phosphatase $< 2 \times$ ULN, AST (SGOT) and ALT (SGPT) $< 3 \times$ ULN;

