9.2. Safety Analyses

Adverse events will be coded using the standard dictionary (MedDRA) down to the lower level term (LLT).

An overall summary table will be presented (Any adverse event, any treatment emergent adverse event (TEAE), any serious adverse event (SAE) including serious adverse drug reactions (SARs) and suspected unexpected serious adverse reactions (SUSARs), death, any grade 3 or higher adverse events from baseline to the end of Study).

Two periods will be defined for TEAE:

- Any adverse event which occurs or worsens from first dosing to Day 28;
- Any adverse event which occurs after Day 28.

TEAEs will be described by primary system organ class and preferred term. Numbers and percentage of patients, and number of occurrences of adverse event will be presented for:

- TEAE;
- Serious TEAE;
- TEAE leading to study treatment discontinuation;
- TEAE of grade 3 or 4;
- TEAE for which relationship with the study treatment is recorded as possible or probable.

The assessment of safety will be based on the frequency of adverse events (with and without regard to causality) graded according to the CTC-AE Classification (version 5.0) and also, the review of individual values for clinical laboratory data, vital signs and ECG focusing on the detection of abnormal values and PCSAs [potentially clinically significant abnormalities (PCSAs) determined upon investigator considerations].

Clinical laboratory parameters, vital signs, ECG will be summarized by using descriptive statistics (n, mean, SD, median, minimum and maximum). Number of patients with at least one abnormal value will be tabulated (counts and percentages) for each parameter in summary shift tables, by study treatment group.

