4.2.1 Study Days

The date of Visit 1 is defined as Day 1. All other study days will be labeled relative to Day 1.

For observation/event dates on or after Day 1, study day for an observation/event date is derived as:

- Observation/event date – Visit 1 date + 1 day, which could be Day 1, Day 2, Day 3, etc.

For observation/event dates prior to Day 1, study day for an event date is derived as:

- Observation/event date – First infusion date, which could be Day -1, Day -2, etc., referring to 1 day, 2 days, etc., prior to Day 1, respectively.

Subsequently, Day 0 is not defined.

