4.2.3 Analysis Periods, Visit Windows and Naming

Analysis periods will be derived for the statistical analyses based on the assigned analysis visits. Timing of analysis periods with start and end visits are tabulated in [Table 1](#).

Table 1 Analysis Periods

Analysis Period	Start	End
Treatment Period	Visit 1 (Day 1)	Visit 5
Safety Follow-up Period	Visit 5 + 1 day	Visit 6
Long-term FUP	Visit 6 + 1 day	Visit 7
Overall Study Period	Visit 1 (Day 1)	Visit 7

As patients will not necessarily have their examinations at the exact scheduled visit time, it could be misleading if all data with the same nominal visit number are lumped together for a by-visit analysis. Thus, all post-baseline data (including both scheduled and unscheduled visits) will be “realigned” in the statistical analysis according to the appropriate window schema and according to the following general conventions.

The reference start day of the first visit window in the Treatment Period is Day 1. The start day of all other visit windows up to Visit 5 (Day 28) is the midpoint between the scheduled visit day for the previous visit ($Visit_{(i)}$) and the subsequent visit ($Visit_{(i+1)}$) plus 1 day: $(Visit_{(i)} + Visit_{(i+1)})/2 + 1$.

The end day of a visit window in the Treatment Period is the day prior to the start day of the next visit window with the exception of the last visit window, where the end day of the visit window will be the day of the EoT visit.

Safety Follow-up Period: Visit 6 (EoS) and Visit 7 (Long term FUP) assessments will be realigned utilizing the same general conventions but with the reference start day of the safety follow-up period derived relative to the last available assessment (scheduled or unscheduled) assigned to Treatment Period + 1 day (see [Table 2](#)).

Width of a realigned visit window will depend on the schedule of assessments for the respective type of assessment. That is, $Visit_{(i)}$ and $Visit_{(i+1)}$ day above refer to the visits as scheduled for the respective assessment and unless otherwise specified will be realigned per [Table 2](#) (General realignment of visits).

Multiple assessments within visit windows

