4.3 Handling of Dropouts or Missing Data

4.3.1 Imputation of Missing and Incomplete Dates/Times

Every effort will be made to collect complete dates for all study assessments. The following date imputation rules will be applied for missing or partial dates:

- If month and year available, set start date to latest of (1st of the month, first dose date), if end date is complete and imputed start date > end date, set imputed start date to end date – 1
- If year available: Set start date to latest of (January 1st, first dose date), if end date is complete and imputed start date > end date, set imputed start date to end date – 1
- If start date is completely missing, set to first dose date, if end date is complete and imputed start date > end date, set imputed start date to end date – 1.

Completely missing time information will be imputed as 00:00. Partially missing time information with missing hour (xx:mm) or minute (hh:mm) part will be imputed as 00:mm or hh:00, respectively. Missing part will be shown as NK in the listings (where NK = Not Known).

If time is not collected and date of assessment is the same as the first dose date, then assessment will be assumed to be collected prior to treatment unless schedule of assessments and protocol indicate planned collection is always after dosing.

Any AEs with incomplete start and end dates/times will be treated as follows:

Adverse events with unknown start and/or end times (but where the date is known) will be imputed with a time of 00:00 h for the tabulations but will be shown as NK: NK in the listings (where NK = Not Known).

Adverse events with completely unknown start dates will be considered as treatment-emergent for the tabulations and will be shown as NK in the listings. Partially complete AE dates will not be imputed in the listings and the available day, month and year components will be used to determine if an adverse event is treatment-emergent taking the first dosing date and end of study date as references.

Imputing partial AE and prior/concomitant medication start dates:

- a) If the year is unknown, the date will not be imputed and will be assigned a missing value.
- b) If the month is unknown, then:
 1. If the year matches the first dose date, then impute to the month and day of the first dose date.
 2. Otherwise, assign 'January'.
- c) If the day is unknown, then:
 1. If the month and year match the first dose date, then impute to the day of the first dose date.
 2. Otherwise, assign '01'.

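### SAP 4.11.4 does not limit the any-CS vital-sign table to post-baseline values, and the vital-sign and ECG shift tables of Protocol 9.2 are missing without being declared

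*SAP*

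**What the plan says.** SAP 4.11.4 sets the visits that feed its tables: "Vitals signs, ECG recording will be summarized for all visits scheduled in treatment and follow up periods". For vital signs it then lists three summaries. The first two are by arm and visit: each vital sign with its CS count, and the numeric change from baseline. The third is at patient level: "A summary of the number and percentage of patients with any CS vital sign value in each vital sign parameter by treatment group". It names no period and makes no reference to baseline.

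For ECG there is one summary, built on the investigator's overall interpretation: "A summary of the number and percentage of patients in each category (normal, abnormal NCS and abnormal CS) will be provided by treatment group". This table is split by visit as well. SAP 4.11.4 defines baseline as the last evaluable measurement before the first dose, but neither the any-CS table nor the ECG table uses it.

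SAP 4.2.1 states "The date of Visit 1 is defined as Day 1". SAP 4.2.3 states "The reference start day of the first visit window in the Treatment Period is Day 1", and Table 1 there gives Visit 1 as the start of the Treatment Period. The schedules in both documents mark vital signs and ECG at Visit 1.

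Protocol 9.2 names laboratory parameters, vital signs and ECG together, and continues: "Number of patients with at least one abnormal value will be tabulated (counts and percentages) for each parameter in summary shift tables". These tables are to be split by arm. The protocol synopsis (Statistical Methods) says the same. SAP 4.11.3 specifies shift tables for laboratory parameters. SAP 4.11.4 lists none. SAP 4.13 declares two changes, the removal of the efficacy analyses and the renumbering of Day 0 as Day 1.

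**The concern.** A patient-level count of abnormal values is useful in a safety comparison when it describes what happened after dosing. If it also takes in the pre-dose value, everyone already CS at entry is counted whatever happens later. Randomisation makes that block about equal in the two arms, so it creates no difference on average, but it pulls the ratio towards 1.

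Some entry abnormality is plausible here. One qualifying risk factor is "Recent history of uncontrolled High Blood Pressure", another is a history of ischaemic cardiovascular disease, and fever is among the qualifying symptoms (Protocol 4.2.1).

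For ECG, counts by visit show how many patients are abnormal at that visit. They do not show how many became abnormal. The shift table in Protocol 9.2 would answer that question, and it is not among the outputs in SAP 4.11.4. Since version 4.0 the SAP covers safety only, so these tables are a larger part of the report than they would otherwise have been.

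**Working it through.** The plan states no figure on this point, so there is nothing to reproduce. The check is a comparison of texts, followed by an illustration of size.

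**1. Can a pre-dose value enter the any-CS table?** The table carries no restriction. 4.11.4 covers all scheduled visits of the treatment and follow-up periods. Visit 1 is a scheduled visit, and Table 1 places it inside the Treatment Period. Where an assessment on the first-dose date has no time, SAP 4.3.1 says "then assessment will be assumed to be collected prior to treatment unless schedule of assessments and protocol indicate planned collection is always after dosing". Visit 1 values are therefore mostly treated as pre-dose, and the literal wording lets them count. This is a reading of a silent line combined with Table 1; the SAP does not say outright that Visit 1 is counted.

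**2. Is the shift-table commitment carried over?**

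| Domain | Protocol 9.2 | SAP 4.11.3 / 4.11.4 | Declared in SAP 4.13 |
|---|---|---|---|
| Laboratory | shift table by arm | specified | not needed |
| Vital signs | shift table by arm | none listed | no |
| ECG | shift table by arm | none listed | no |

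**3. Size of the dilution (assumed rates).** Let e be the share of patients CS at entry, equal in both arms, and r the rate of new CS values among the rest. If Visit 1 is counted:

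- share in the table = e + (1 − e) × r
- difference between arms = (1 − e) × (r for ABX464 − r for placebo)

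Assumption A: r = 10% on ABX464 and 5% on placebo (true ratio 2.00).

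| e | ABX464 | Placebo | Ratio | Difference (points) |
|---|---|---|---|---|
| 0% | 10.0% | 5.0% | 2.00 | 5.0 |
| 5% | 14.5% | 9.75% | 1.49 | 4.75 |
| 10% | 19.0% | 14.5% | 1.31 | 4.5 |
| 20% | 28.0% | 24.0% | 1.17 | 4.0 |
| 30% | 37.0% | 33.5% | 1.10 | 3.5 |

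Example at e = 10%: 0.10 + 0.90 × 0.10 = 0.190; 0.10 + 0.90 × 0.05 = 0.145; 0.190 / 0.145 = 1.31.

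Assumption B: r = 6% and 2% (true ratio 3.00).

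| e | ABX464 | Placebo | Ratio | Difference (points) |
|---|---|---|---|---|
| 10% | 15.4% | 11.8% | 1.31 | 3.6 |
| 30% | 34.2% | 31.4% | 1.09 | 2.8 |
| 40% | 43.6% | 41.2% | 1.06 | 2.4 |

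The difference in each row is the excess of newly CS patients expressed over all patients, so it is not lost. Counted among patients not CS at entry, the ratio stays at 2.00 or 3.00 whatever e is. These percentages do not depend on the arm sizes. No power figure is given because SAP 4.11.4 plans no test on these tables.

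**4. ECG by visit (assumed rates).** Take 40% abnormal at baseline, 90% of those still abnormal at a later visit, and new abnormality in 6% (ABX464) and 2% (placebo) of the rest. The later visit shows:

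- ABX464: 0.40 × 0.90 + 0.60 × 0.06 = 39.6%
- placebo: 0.40 × 0.90 + 0.60 × 0.02 = 37.2%

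Both arms sit slightly below their 40% at Visit 1, and the ratio reads 39.6 / 37.2 = 1.06, although new abnormality is three times as frequent on ABX464. The by-visit table cannot recover that ratio. A cross-tabulation with baseline gives it directly.

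**The case against.** The strongest reply is that new findings are reported elsewhere, and relative to baseline. Protocol 5.3.1 requires CS vital-sign excursions to be recorded as adverse events. Protocol 5.3.4 requires the same for clinically relevant ECG findings compared with Day 0. SAP 4.11.1 counts an event as treatment-emergent only if it begins or worsens after dosing, and tabulates such events by arm. SAP 4.11.4 itself adds by-visit CS counts in which Visit 1 can be seen separately, numeric change from baseline for vital signs, and by-patient listings. This stands. A reader might infer that new abnormalities are hidden; the documents do not support that.

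A reader might also infer that ECG abnormality present at entry is reported as an on-study finding. It is not, because the ECG table is by visit and entry ECGs fall under Visit 1. What remains is that new and persisting abnormality cannot be told apart afterwards.

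Nor do the entry criteria show that many baseline values will be CS. Fever, recent hypertension history and ischaemic history are alternatives among several symptoms and risk factors, and none of them is a CS reading at Visit 1.

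Finally, SAP 4.2.4 allows shift tables for categorical change where appropriate. That leaves room for the missing tables but commits to none in 4.11.4, whereas Protocol 9.2 does commit. Listings are not arm comparisons, and the adverse-event route depends on the investigator reporting the change. These safeguards lessen the consequence of the gap without closing it.

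**Conclusion.** The point holds as a modest defect in descriptive safety tables. Three things follow from the text without assumptions: the any-CS table has no post-baseline limit while Visit 1 lies in the Treatment Period; the ECG summary has no comparison with baseline; and the vital-sign and ECG shift tables of Protocol 9.2 are absent from SAP 4.11.4 and not declared in 4.13.

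The direction of the effect is also clear. Counting entry values dilutes the ratio between arms, keeps the absolute excess among patients not CS at entry, and creates no difference on average. Its size is not known. The ratios above rest on assumed entry prevalence and onset rates, because the documents give none. The conclusion that Visit 1 is counted rests on a literal reading of a line that is silent on the matter. It would be wrong to conclude that these tables mainly describe who was enrolled, or that a drug effect is concealed.

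**What to change.** In SAP 4.11.4:

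1. Limit the any-CS vital-sign table to values after the first dose, and show it by baseline status (CS / not CS) for each parameter and arm. Use the pre-first-dose baseline that 4.11.4 already defines, with the 4.3.1 rule for untimed values on the day of first dose.
2. Add an ECG shift table by arm, from baseline category (normal, abnormal NCS, abnormal CS) to post-baseline category. Protocol 9.2 does not prescribe the layout, so either by visit or worst post-baseline would meet it.

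If the sponsor prefers to leave out either shift table, 4.13 should say so and give the reason.

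The cost is SAP wording and two extra tables from data already collected. No protocol amendment, new data or patient burden is involved.

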4.11.5 Safety Monitoring (Data and Safety Monitoring Board [DSMB])

A Data and Safety Monitoring Board (DSMB) will monitor study results, evaluates the treatments for excess adverse effects, determines whether the basic trial assumptions remain valid, judges whether the overall integrity and conduct of the trial remain acceptable, and makes recommendations to the Abivax study team and to the study principal investigator. The justification for the establishment of the DSMB and the grounds for stopping/continuing studies, as well as the DSMB procedures is provided in the DSMB charter.

The DSMB will be responsible for interpreting the results of periodic safety analyses. Tables, listings, and figures (TLFs) provided for the DSMB will be created by the blinded statistical team (biostatisticians and statistical programmers) using dummy treatment codes and will be passed to the unblinded statistical team who will apply the true treatment codes in a secure manner. Blinded and unblinded directories will be maintained and access to the unblinded directory will be restricted to the unblinded team member until database lock and study unblinding. All TLFs (planned and ad-hoc) created for the DSMB will be developed following the guidelines defined in this SAP, as appropriate. Specifications for these outputs will be included and marked in the TLF shells developed to support the clinical study report.

4.12 Determination of Sample Size

For the sample size / power calculation, the following assumptions are made:

- Primary efficacy endpoint response probability for Standard of Care + ABX464: 84 %
- Primary efficacy endpoint response probability for Standard of Care + placebo: 75 %
- Type 1 error probability: 2.5% one -sided.
- 2:1 (ABX464 50mg: placebo) study treatment allocation ratio.
- One interim analysis after approximately 300 patients complete Day 28 assessment or reach end of study: non-binding futility criterion is a conditional power (calculated under observed effect) $\leq 10\%$.

If the above assumptions hold true, then an initial total sample size of 800 patients will lead to a power of 78%. Sample size re-assessment and potential increase to 1034 patients is described in Section **Error! Reference source not found.**

All sample size calculations were performed using EAST 6.5

4.13 Changes in the Conduct of the Study or Planned Analysis

1) As part of data and safety monitoring per protocol, a data and safety monitoring board (DSMB) meeting held on 04 March 2021 concluded to study futility and recommended study termination. As sequel to DSMB recommendation sponsor terminated the study due to futility and initiated the

reporting of study result in an abbreviated manner. In accordance with this decision the following changes to the planned analyses are being introduced.

Efficacy results and related analyses are not in the scope of SAP (Section 1). Consequently, the following endpoint will not be derived and/or analyzed:

i) Primary endpoint defined as:

Rate of patients who do not require use of high-flow oxygen (use of high-flow oxygen being defined as settings of 3 L/min or greater AND with at least one SpO₂ measurement < 92%, with or without O₂ supplementation) or, invasive or non-invasive mechanical ventilation (IMV and NIV, respectively) within 28 days and who are alive at the end of the 28 days period.

ii) Secondary endpoint defined as:

Rate of patients hospitalized, Time to hospitalization from baseline, Number of days at the hospital from admission to discharge;

Seven-point ordinal scale: By visit summaries for percentage of patients in each severity category and Change from baseline in the scale rank, Time to improvement of one level in 7-point ordinal scale;

% change and AUC over time of oxygen saturation measured by daily pulse oximetry before hospitalization;

Rate of patients with SpO₂ ≤ 94% and rate of patients with SpO₂ ≤ 92% at Day 28;

Change from enrolment in inflammatory markers in plasma (i.e. MCP-1, MIP-1 α , G-CSF, IL-1b, IL-2, IL-6, IL-7, IL-10, IL-17, INF γ and TNF α) and in immune phenotype and assessment of cell-activation markers in PBMCs at D14, D28;

Rate of patients requiring oxygen supplementation, Time to assisted ventilation and oxygen supplementation (log rank) from baseline, Number of days of assisted ventilation, Number of days of oxygen supplementation;

Change from baseline in microRNA-124 levels in total blood (PAXgene®) at D0, D7 and D28;

AUC and % of change from enrolment in CRP, Troponin I & T and D-dimer levels;

Time to death and mortality rate (all causes, and Covid-19 related);

SARS-CoV-2 virus in nasopharyngeal sample and/or in blood at Day 0, 7 (hospitalized patients), 14, 21, and 28;

Change in SpO2 values from D0 to D14 in the outpatient's population,

Rate of participants deceased during the course of the study and follow-up, and time to event (in weeks).

i) Exploratory endpoints defined as:

Central blinded review of the hospitalization discharge CT-Scans for descriptive analysis with regards to the disease severity and outcomes.

Change from last dosing day in the Medical Research Council (MRC) dyspnea scale in the hospitalized patient's population according to treatment group.

Optional: Change from last dosing day in Pulmonary Function Tests (PFT) (Forced Expiratory Volume (FEV) and slow and forced Vital Capacity (VC)) and Carbon Monoxide Diffusing Capacity (CMDC) tests in the hospitalized patient's population according to treatment group.

2) Study day definition is changed as the date of Visit 1 is defined as Day 1 not Day 0 as it is in the protocol. All other study days will be labeled relative to Day 1.

